14.2.1.7 Plasma concentration of albendazole for Test Product-T1 (first administration)

Lambda Therapeutic Research Ltd.

Confidential

Project No. 0110-23

Table 14.2.1.7

		oncentration of oduct-T1 (first a										
Time		Participan	ts		N	Mean	SD	Min	Median	Max	CV%	Geometric
(unit)		Concentration	(unit)									Mean
	1001	1002	•	n								
T_1	XX.XXX	XX.XXX		XX.XXX	XX	x.xxx	x.xxxx	x.xxx	x.xxx	x.xxx	X.X	X.XXX
T_2	XX.XXX	XX.XXX		XX.XXX	XX	x.xxx	x.xxxx	x.xxx	x.xxx	x.xxx	x.x	x.xxx
•									•			
•	•	•		•	•	•		•	•	•	•	
				•				•	•	•		
•								•	•	•		
	•	•		•	•	•	•	•	•	•	•	
Ti	XX.XXX	XX.XXX		XX.XXX	XX	X.XXX	X.XXXX	X.XXX	X.XXX	X.XXX	X.X	X.XXX

Note: Here T_i ($i = 1, 2, \ldots, n$) denotes the time points at which blood sample has been taken

<Note 1: Repeat the same table as 14.2.1.8 for Test Product-T2 (second administration), 14.2.1.9 for Reference Product-R1 (first administration) and 14.2.1.10 for Reference Product-R2 (second administration) of albendazole.>

<Note 2: Repeat the same table as 14.2.2.7 for Test Product-T1 (first administration), 14.2.2.8 for Test Product-T2 (second administration), 14.2.2.9 for Reference Product-R1 (first administration) and 14.2.2.10 for Reference Product-R2 (second administration) of albendazole sulfoxide.>

14.2.1.11 Plasma concentration of data excluded from statistical analysis for albendazole (if applicable)

Lambda Therapeutic Research Ltd.

Confidential
Table 14 2 1 11

Project No. 0110-23

		1able 14.2.1.11							
	Plasma concentration of	Plasma concentration of data excluded from statistical analysis for albendazole							
		Participants							
Time (h)		Concentration (unit)							
Time (ii)	1001	1002		n					
	Period	Period		Period					
	Formulation	Formulation		Formulation					
T_1	XX.XXX	XX.XXX		XX.XXX					
T_2	XX.XXX	XX.XXX		XX.XXX					
•	•	•							
•	•	•							
•	•	•	•						
T_{i}	XX.XXX	XX.XXX	•	XX.XXX					

Note: Here T_i ($i = 1, 2, \ldots, n$) denotes the time points at which blood sample has been taken.

<Note: Repeat the same table as 14.2.2.12 for albendazole sulfoxide.>

14.2.3 Actual time points used for pharmacokinetic evaluation

Lambda Therapeutic Research Ltd.

Confidential

Project No. 0110-23

Table 14.2.3

Actual time points used for pharmacokinetic evaluation

Participants	Period	Time Point (unit)	Difference in Minutes	Difference in Hour	Actual Time of Collection (unit)
1001		x.xxx		x.xxx	x.xxx
1002		x.xxx		x.xxx	x.xxx
•		•		•	
		•		•	
•		•		•	
•		•		•	
•		•		•	
•		•		•	
•		•		•	
•		•		•	•
n		x.xxx		X.XXX	x.xxx

14.3 Safety Data

14.3.1 Overall summary of treatment emergent adverse events (Safety set)

Lambda Therapeutic Research Ltd.

Confidential

Project No. 0110-23

Table 14.3.1

	Test Treatment-T	Reference Treatment-R	Total	
	(N=xx)	(N=xx)	(N=xx)	p-valu
	n (%) e	n (%) e	n (%) e	
At least one TEAE	xx (xx.x) xx	xx (xx.x) xx	xx (xx.x) xx	x.xxx
At least one TEAE leading to discontinuation	xx (xx.x) xx	xx (xx.x) xx	xx (xx.x) xx	X.XXX
At least one TESAE	xx (xx.x) xx	xx (xx.x) xx	xx (xx.x) xx	_
Assessment of intensity				_
Mild	xx (xx.x) xx	xx (xx.x) xx	xx (xx.x) xx	
Moderate	xx (xx.x) xx	xx (xx.x) xx	xx (xx.x) xx	
Severe	xx (xx.x) xx	xx (xx.x) xx	xx (xx.x) xx	
Seriousness criteria				-
Congenital Anomaly/Birth Defect	xx (xx.x) xx	xx (xx.x) xx	xx (xx.x) xx	
Hospitalization or prolongation of existing	xx (xx.x) xx	xx (xx.x) xx	xx (xx.x) xx	
hospitalization	xx (xx.x) xx	xx (xx.x) xx	xx (xx.x) xx	
Result in persistent or Significant	xx (xx.x) xx	xx (xx.x) xx	xx (xx.x) xx	
Disability/incapacity	AA (AA.A) AA	AA (AA.A) AA	AA (AA.A) AA	
Life threatening	xx (xx.x) xx	xx (xx.x) xx	xx (xx.x) xx	
Abnormal pregnancy outcomes	xx (xx.x) xx	xx (xx.x) xx	xx (xx.x) xx	
Death	xx (xx.x) xx	xx (xx.x) xx	xx (xx.x) xx	
Other Medically Important Event	xx (xx.x) xx	xx (xx.x) xx	xx (xx.x) xx	
Relationship to Study Treatment				_
Related				
Certain	xx (xx.x) xx	xx (xx.x) xx	xx (xx.x) xx	
Probable/Likely	xx (xx.x) xx	xx (xx.x) xx	xx (xx.x) xx	
Possible	xx (xx.x) xx	xx (xx.x) xx	xx (xx.x) xx	
Not Related				
Unlikely	xx (xx.x) xx	xx (xx.x) xx	xx (xx.x) xx	
Conditional/Unclassified	xx (xx.x) xx	xx (xx.x) xx	xx (xx.x) xx	

Lambda Therapeutic Research Ltd.

Confidential Table 14.3.1

Project No. 0110-23

Overall summary of treatment emergent adverse events (Safety set)

	Test Treatment-T	Reference Treatment-R	Total	
	(N=xx)	(N=xx)	(N=xx)	p-value
	n (%) e	n (%) e	n (%) e	
Unassessable/Unclassifiable	xx (xx.x) xx	xx (xx.x) xx	xx (xx.x) xx	
Unrelated	xx (xx.x) xx	xx (xx.x) xx	xx (xx.x) xx	
Action Taken with Study Treatment				_
Dose Increased	xx (xx.x) xx	xx (xx.x) xx	xx (xx.x) xx	
Dose Not Changed	xx (xx.x) xx	xx (xx.x) xx	xx (xx.x) xx	
Dose Reduced	xx (xx.x) xx	xx (xx.x) xx	xx (xx.x) xx	
Drug Interrupted	xx (xx.x) xx	xx (xx.x) xx	xx (xx.x) xx	
Drug Withdrawn	xx (xx.x) xx	xx (xx.x) xx	xx (xx.x) xx	
Not Applicable	xx (xx.x) xx	xx (xx.x) xx	xx (xx.x) xx	
Unknown	xx (xx.x) xx	xx (xx.x) xx	xx (xx.x) xx	
Outcome				_
Not Recovered/Not Resolved	xx (xx.x) xx	xx (xx.x) xx	xx (xx.x) xx	
Recovering/resolving	xx (xx.x) xx	xx (xx.x) xx	xx (xx.x) xx	
Recovered/Resolved	xx (xx.x) xx	xx (xx.x) xx	xx (xx.x) xx	
Recovered/Resolved With Sequelae	xx (xx.x) xx	xx (xx.x) xx	xx (xx.x) xx	
Stable	xx (xx.x) xx	xx (xx.x) xx	xx (xx.x) xx	
Change in severity	xx (xx.x) xx	xx (xx.x) xx	xx (xx.x) xx	
Fatal	xx (xx.x) xx	xx (xx.x) xx	xx (xx.x) xx	
Converted to SAE	xx (xx.x) xx	xx (xx.x) xx	xx (xx.x) xx	
Unknown	xx (xx.x) xx	xx (xx.x) xx	xx (xx.x) xx	
Death	xx (xx.x) xx	xx (xx.x) xx	xx (xx.x) xx	

N = Number of subjects in respective treatment population.

Reference Listing: 16.2.7.1

n = Number of subjects in respective categories; e = Number of events.

Percentages are based on the number of subjects allocated to each category.

P-value is calculated based on a chi-square test. If any cell has expected counts less than 5, then the Fisher's exact test is used instead.

14.3.2 Summary of treatment emergent adverse events by system organ class and preferred term (Safety set)

Lambda Therapeutic Research Ltd.

Confidential

Project No. 0110-23

Table 14.3.2

Summary of treatment emergent adverse events by system organ class and preferred term (Safety set)

	Test Treatment-T	Reference Treatment-R	Total
System Organ Class	(N=xx)	(N=xx)	(N=xx)
Preferred Term	n (%) e	n (%) e	n (%) e
Subjects with At least one TEAE	xx (xx.x) xx	xx (xx.x) xx	xx (xx.x) xx
System Organ Class 1	xx (xx.x) xx	xx (xx.x) xx	xx (xx.x) xx
Preferred Term 1	xx (xx.x) xx	xx (xx.x) xx	xx (xx.x) xx
Preferred Term 2	xx (xx.x) xx	xx (xx.x) xx	xx (xx.x) xx
•			
•			
System Organ Class 2	xx (xx.x) xx	xx (xx.x) xx	xx (xx.x) xx
Preferred Term 1	xx (xx.x) xx	xx (xx.x) xx	xx (xx.x) xx
Preferred Term 2	xx (xx.x) xx	xx (xx.x) xx	xx (xx.x) xx
Etc.			

N = Number of subjects in respective treatment population.

n = Number of subjects in respective categories; e = Number of events.

Percentages are based on the number of subjects allocated to each category.

Each subjects is counted at the most once within each PT.

Adverse Events are coded using Medical Dictionary for Regulatory Activities (MedDRA) version xx

Reference Listing: 16.2.7.1

Project No. 0110-23 Version 00

14.3.3 Summary of treatment emergent adverse events by relationship to study drug and system organ class and preferred term (Safety set)

Lambda Therapeutic Research Ltd.

Confidential

Project No. 0110-23

Table 14.3.3

Summary of treatment emergent adverse events by relationship to study drug and system organ class and preferred term (Safety set)

System Organ Class Preferred Term	(N=	atment-T xxx) %) e	(N=	Treatment-R =xx) %) e	Total (N=xx) n (%) e		
	Related	Not-Related	Related	Not-Related	Related	Not-Related	
Subjects with At least one TEAE	xx (xx.x) xx	xx (xx.x) xx	xx (xx.x) xx	xx (xx.x) xx	xx (xx.x) xx	xx (xx.x) xx	
System Organ Class 1	xx (xx.x) xx	xx (xx.x) xx	xx (xx.x) xx	xx (xx.x) xx	xx (xx.x) xx	xx (xx.x) xx	
Preferred Term 1	xx (xx.x) xx	xx (xx.x) xx	xx (xx.x) xx	xx (xx.x) xx	xx (xx.x) xx	xx (xx.x) xx	
Preferred Term 2	xx (xx.x) xx	xx (xx.x) xx	xx (xx.x) xx	xx (xx.x) xx	xx (xx.x) xx	xx (xx.x) xx	
· ·							
	xx (xx.x) xx	xx (xx.x) xx	()	()	()	xx (xx.x) xx	
System Organ Class 2	, ,	,	xx (xx.x) xx	xx (xx.x) xx	xx (xx.x) xx	•	
Preferred Term 1	xx (xx.x) xx	xx (xx.x) xx	xx (xx.x) xx	xx (xx.x) xx	xx (xx.x) xx	xx (xx.x) xx	
Preferred Term 2	xx (xx.x) xx	xx (xx.x) xx	xx (xx.x) xx	xx (xx.x) xx	xx (xx.x) xx	xx (xx.x) xx	
Etc.							

N = Number of subjects in respective treatment population.

n = Number of subjects in respective categories; e = Number of events.

Percentages are based on the number of subjects allocated to each category.

Each subject is counted at most once within each PT.

Adverse Events are coded using Medical Dictionary for Regulatory Activities (MedDRA) version xx

Reference Listing: 16.2.7.1

14.3.4 Summary of treatment emergent adverse events by severity grade and system organ class and preferred term (Safety set)

Lambda Therapeutic Research Ltd.

Confidential

Project No. 0110-23

Table 14.3.4

Summary of treatment emergent adverse events by severity grade and system organ class and preferred term (Safety set)

	Test Treatment-T	Reference Treatment-R	Total
System Organ Class	(N=xx)	(N=xx)	(N=xx)
Preferred Term	n (%) e	n (%) e	n (%) e
Subjects with At least one TEAE	xx (xx.x) xx	xx (xx.x) xx	xx (xx.x) xx
Mild			
System Organ Class 1	xx (xx.x) xx	xx (xx.x) xx	xx (xx.x) xx
Preferred Term 1	xx (xx.x) xx	xx (xx.x) xx	xx (xx.x) xx
Preferred Term 2	xx (xx.x) xx	xx (xx.x) xx	xx (xx.x) xx
•			
•			
System Organ Class 2	xx (xx.x) xx	xx (xx.x) xx	xx (xx.x) xx
Preferred Term 1	xx (xx.x) xx	xx (xx.x) xx	xx (xx.x) xx
Preferred Term 2	xx (xx.x) xx	xx (xx.x) xx	xx (xx.x) xx
Etc.			

N = Number of subjects in respective treatment population.

n = Number of subjects in respective categories; e = Number of events.

Percentages are based on the number of subjects allocated to each category.

Each subject is counted at most once within each PT.

Adverse Events are coded using Medical Dictionary for Regulatory Activities (MedDRA) version xx Reference Listing: 16.2.7.1

Project No. 0110-23

Lambda Therapeutic Research Ltd. Statistical Analysis Plan (SAP) Albendazole Tablets IP 400 mg

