9.4.4. Safety Analysis

Safety data will be presented in tabular and/or listing format and summarized descriptively. Number and percentage will be presented for incidence of AE.

Descriptive statistics (N, n, mean, SD, median, minimum and maximum) will be presented for absolute and change from baseline values of vital signs parameters at each timepoint.

Comprehensive description for statistical analyses of safety endpoints will be described in the SAP.

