10.3.5.3. Assessment of causality

Causality term	Assessment criteria			
	• Event or laboratory test abnormality, with plausible time relationship to drug intake			
Certain	Cannot be explained by disease or other drugs			
	• Response to withdrawal plausible (pharmacologically, pathologically)			
	• Event definitive pharmacologically or phenomenologically (i.e.			

TMF-16298784	Protocol Version No. 1.0			
	an objective and specific medical disorder or a recognized pharmacological phenomenon)			
	Rechallenge satisfactory, if necessary			
	• Event or laboratory test abnormality, with reasonable time relationship to drug intake			
Probable/Likely	Unlikely to be attributed to disease or other drugs			
	Response to withdrawal clinically reasonable			
	Rechallenge not required			
Possible	• Event or laboratory test abnormality, with reasonable time relationship to drug intake			
1 0331610	Could also be explained by disease or other drugs			
	Information on drug withdrawal may be lacking or unclear			
Unlikely	• Event or laboratory test abnormality, with a time to drug intake that makes a relationship improbable (but not impossible)			
	Disease or other drugs provide plausible explanations			
Conditional/	Event or laboratory test abnormality			
TY 1 .00 1	More data for proper assessment needed, or			
Unclassified	Additional data under examination			
Unassessable/	Report suggesting an adverse reaction			
• Cannot be judged because information is insuff contradictory				
	Data cannot be supplemented or verified			
	The adverse event is clearly NOT related to the investigational medicinal product			
Unrelated	A clinical event with an incompatible time relationship and which could be explained by underlying disease or other drugs or chemicals			

• The investigator is obligated to assess the relationship between study intervention and each occurrence of each AE/SAE. The investigator will use clinical judgment to determine the relationship.

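### SAP shell 14.3.1 lists two undetermined causality ratings under Not Related; if shell 14.3.3 follows it, related TEAEs may be understated

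*SAP*

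**What the plan says.** Protocol 10.3.5.3 gives the investigator seven causality terms: Certain, Probable/Likely, Possible, Unlikely, Conditional/Unclassified, Unassessable/Unclassifiable and Unrelated. It does not divide them into related and not related.

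The definitions that matter here are these:

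- Conditional/Unclassified: "More data for proper assessment needed, or" further data are being examined.
- Unassessable/Unclassifiable: a "Report suggesting an adverse reaction", which cannot be judged, and for which "Data cannot be supplemented or verified".
- Unrelated: "The adverse event is clearly NOT related to the investigational medicinal product".

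The two-way split appears only in the SAP table shells. Shell 14.3.1 puts Certain, Probable/Likely and Possible under Related. Under Not Related it puts Unlikely, "Conditional/Unclassified", "Unassessable/Unclassifiable" and Unrelated. The block runs over a page break, but Unrelated follows the Unassessable row, so that row is still in the Not Related block.

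Shell 14.3.3 tabulates TEAEs by relationship, system organ class and preferred term. For each product and in total it has a Related and a Not-Related column. None of its footnotes says which of the seven terms feeds which column.

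SAP 7.2 gives no grouping rule, and SAP Section 8 lists only the ANOVA model as a change from the protocol.

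**The concern.** A two-column summary of causality is read as events attributed to the drug versus events judged not to be. A rating that means the investigator could not decide, or has not yet decided, belongs in neither column. Placing it under Not Related turns missing information into a negative judgement that the protocol's definitions do not make.

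What is at stake is the descriptive picture of drug-attributed events by product. Safety and tolerability of test versus reference is a secondary objective, and 14.3.3 is the planned table that shows related events by system organ class and preferred term. If undetermined events are folded into Not-Related there, a reader of that table cannot see that they were undetermined.

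**Working it through.** The documents give no event counts, so there is no planned figure to reproduce. The check sets the protocol definitions beside the SAP grouping and then works out the possible shift in symbols.

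**Step 1. Term by term**

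| Term | Sense of the definition in protocol 10.3.5.3 | Block in SAP shell 14.3.1 |
|---|---|---|
| Certain | Relationship affirmed | Related |
| Probable/Likely | Relationship favoured | Related |
| Possible | Relationship plausible, other causes too | Related |
| Unlikely | Relationship improbable | Not Related |
| Conditional/Unclassified | Pending, neither affirmed nor denied | Not Related |
| Unassessable/Unclassifiable | Suggested, but cannot be judged | Not Related |
| Unrelated | Relationship denied | Not Related |

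Five of the seven placements follow the sense of the definition. The other two do not: they carry no negative judgement, yet they sit in the negative block.

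**Step 2. Where information would be lost**

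In 14.3.1, Related and Not Related are bare headings without counts, and each of the seven terms has its own row for test, reference and total. A reader can regroup the rows. Listing 16.2.7.1 also keeps the relationship rating for each event. Only 14.3.3 collapses the ratings. The grouping in 14.3.1 is the only one in either document, so it is the likely source for 14.3.3, but the SAP does not say so.

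**Step 3. Size and direction in 14.3.3, if the 14.3.1 grouping is used**

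For one product, let R be the number of events rated Certain, Probable/Likely or Possible; L those rated Unlikely; C Conditional; U Unassessable; and N Unrelated.

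- Grouping as in 14.3.1: Related = R; Not-Related = L + C + U + N.
- Undetermined ratings shown apart: Related = R; Undetermined = C + U; Not-Related = L + N.
- Both undetermined ratings counted as related, as an upper bound: Related = R + C + U; Not-Related = L + N.

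The Not-Related column therefore holds (L + C + U + N) − (L + N) = C + U events that nobody judged negative. The Related column may fall short by between 0 and (R + C + U) − R = C + U. The shift goes one way only: it can lower Related and raise Not-Related, never the reverse. It is zero when C = U = 0. The bound is in events. The participant counts in the same cells can move by no more than that, because each participant is counted at most once within a preferred term.

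**Step 4. What does not move**

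The total R + L + C + U + N is the same under every grouping, so overall AE incidence in 14.3.1 and 14.3.2 is unchanged. The relationship block of 14.3.1 carries no p-value, and 14.3.3 has no p-value column. Cmax, AUC(0-t), alpha and sample size are not involved.

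**The case against.** The strongest reply has four parts.

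- **The table that contains the grouping hides nothing.** This stands. The possible loss is confined to 14.3.3, and even there it depends on a grouping that the SAP leaves unstated.
- **The protocol never divides the seven terms into two classes, so the SAP breaks no protocol rule.** This also stands. A reader might infer that every event in the two categories is misclassified, or that both should count as related. The documents do not support either reading. Conditional contains no suggestion of a drug cause, and Unassessable suggests one but says it cannot be judged. Counting them as related would also turn unknown into known. This argument does not defend the present heading, however: it points to a third class.
- **The categories may be empty at analysis.** The investigator must assess the relationship of every AE (protocol 10.3.5.3), must give causality with each initial SAE report (8.4.4), and has participants housed for at least 24 hours after each dose (4.1). Conditional is provisional by nature. This limits the likely size but does not bring it to zero. Unassessable is permanent by its own definition, and nothing in the SAP requires Conditional ratings to be resolved before analysis. Protocol 10.3.5.5 lets non-serious AEs be followed until 12 months after the study ends, while 10.1.7 targets results summaries within 12 months of completion, so some ratings could still be pending.
- **Related-AE incidence is not an endpoint.** This is correct. The safety endpoints are AE incidence and vital signs, and protocol 9.4.4 says "Safety data will be presented in tabular and/or listing format and summarized descriptively". A reader might infer a biased comparison of test with reference. Nothing in the documents shows one: the same grouping would apply to both products, and there are no counts from which to derive a difference.

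**Conclusion.** The point holds in a limited form. Shell 14.3.1 labels two undetermined ratings as Not Related, without a basis in the protocol's definitions and without a stated reason. If 14.3.3 follows that grouping, related TEAEs may be understated there by 0 up to C + U events, and not-related TEAEs overstated by C + U.

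This rests on two assumptions: that the 14.3.1 grouping carries over to 14.3.3, and that at least one event still has one of the two ratings at analysis. The documents cannot settle either. It would therefore go too far to say that treatment-related events are under-counted as a matter of fact.

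Severity is low. The effect is confined to how a descriptive table is read, and the correct information can be recovered from 14.3.1 (overall) and listing 16.2.7.1 (by event).

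**What to change.** Three edits, made before the results are seen:

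1. In shell 14.3.1, move the two rows out of Not Related to a separate heading, *Causality undetermined (pending / not assessable)*.
2. In shell 14.3.3, add a matching third column for each product and for the total.
3. In SAP 7.2, and in a footnote to 14.3.3, state the mapping: Certain, Probable/Likely and Possible to Related; Unlikely and Unrelated to Not Related; Conditional/Unclassified and Unassessable/Unclassifiable to Undetermined.

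The cost is two shell edits, a sentence in SAP 7.2 with its footnote, and a mapping line in the program. No new data are needed. Settling the rule in advance also avoids choosing it after the ratings are known in an open-label study.

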14.3.5 Summary of subject disposition

Lambda Therapeutic Research Ltd.

Confidential

Table 14.3.5

Summary of subject disposition

	TRTR	RTRT	Total
	(N=xx)	(N=xx)	(N=xx)
	n (%)	n (응)	n (%)
Subjects Randomized	xx (xx.x)	xx (xx.x)	xx (xx.x)
Subjects included in Safety set	xx (xx.x)	xx (xx.x)	xx (xx.x)
Subjects included in PK set	xx (xx.x)	xx (xx.x)	xx (xx.x)
Subjects who completed study	xx (xx.x)	xx (xx.x)	xx (xx.x)
Subjects who discontinued study	xx (xx.x)	xx (xx.x)	xx (xx.x)
Reason for discontinuing study			
Reason 1	xx (xx.x)	xx (xx.x)	xx (xx.x)
Reason 2	xx (xx.x)	xx (xx.x)	xx (xx.x)
Reason 3	xx (xx.x)	xx (xx.x)	xx (xx.x)
Etc.	xx (xx.x)	xx (xx.x)	xx (xx.x)

N = Number of subjects in safety set, n = Number of subjects in respective categories Note: Percentages are calculated based on the total number of subjects in each category. Treatment specification \rightarrow T = Test Product and R = Reference Product. Reference Listing: 16.2.1.2

Output Generated on: DDMMMYYYY hh:mm

<Note for programmers: Reason for discontinued should be in descending order i.e., highest reported reasons should come first.>

14.3.6 Summary of vital signs (Safety set)

Lambda Therapeutic Research Ltd.

Confidential

Project No. 0110-23

Table 14.3.6

Summary of vital signs (Safety set)

Parameters (Unit)	Visit (Day)	Time Point	Statistics	TRTR (N=xx)	RTRT (N=xx)	Total (N=xx)	p-value
Pulse rate (beats/min)	Screening		n Mean (SD) Median Min, Max	xx xx.x (xx.xx) xx.x xx.x, xx.x	xx xx.x (xx.xx) xx.x xx.x, xx.x	xx xx.x (xx.xx) xx.x xx.x, xx.x	x.xxx
	Assessment Visit X	Time Point 1	n Mean (SD) Median Min, Max	xx xx.x (xx.xx) xx.x xx.x, xx.x	xx xx.x (xx.xx) xx.x xx.x, xx.x	xx xx.x (xx.xx) xx.x xx.x, xx.x	x.xxxx
		Time Point 2	n Mean (SD) Median Min, Max	xx xx.x (xx.xx) xx.x xx.x, xx.x	xx xx.x (xx.xx) xx.x xx.x, xx.x	xx xx.x (xx.xx) xx.x xx.x, xx.x	x.xxxx
	Assessment Visit Y	Time Point 1	n Mean (SD) Median Min, Max	xx xx.x (xx.xx) xx.x xx.x, xx.x	xx xx.x (xx.xx) xx.x xx.x, xx.x	xx xx.x (xx.xx) xx.x xx.x, xx.x	x.xxxx
Etc.	Etc.	Etc.	,	. ,	. ,	. ,	

N = Number of subjects in safety set, n = Number of subjects in respective categories

P-value is calculated using an independent t-test.

Treatment specification \rightarrow T = Test Product and R = Reference Product.

Reference Listing: 16.2.9.4

Output Generated on: DDMMMYYYY hh:mm

<Note for programmers: This table will continue for vital parameters like Systolic Blood Pressure (mmHg), Diastolic Blood Pressure (mmHg), Oral Body Temperature (°F), etc.>

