1.2. Schema

Based on US FDA guidance, this study will employ 2 sequences in a 4-period cross-over design, i.e. T-R-T-R and R-T-R-T (T=test study intervention, R=reference study intervention).

Figure 1 Study design overview

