8.3.2. Vital signs

• Vitals (sitting blood pressure and radial pulse) will be recorded at pre-dose (within 60 minutes before the dosing) and at 2, 4, 6, 12 and 24 hours post-dose in each period.

TMF-16298784 Protocol Version No. 1.0

Note: All post-dose vitals will be performed within \pm 40 minutes of the scheduled time.

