6.2 Multiplicity Adjustment

No multiplicity adjustment is required for this bioequivalence study.

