7.2 Safety Analysis

Safety analysis will be done on the safety set. Safety variables include AEs, clinical laboratory parameters, vital signs, physical examinations. Safety variables will be listed and summarized with descriptive statistics as appropriate.

Continuous variables will be Summarized by treatment/sequence group using summary statistics (number of observations, mean, standard deviation, median, minimum and maximum etc.) as applicable. Categorical values will be summarized by the treatment group using frequencies and percentages.

Result obtained when evaluating safety (adverse events, vital signs, clinical laboratory tests etc.) will be listed and evaluated descriptively.

Adverse events

All AEs reported during the study must be included in the safety analysis. AEs will be classified by system organ class, by preferred term from the MedDRA version 25.0 or higher. They will be presented in individual listings and summary tables, and evaluated descriptively and in terms of

frequencies, by treatment. As will be summarized for all subjects in Safety set across two treatment groups by System Organ Class (SOC) and Preferred Term (PT). p-value using chi-square test or fisher exact test will be provided for the AE data.

Intensity refers to the severity of the AE.: Mild, Moderate, Severe.

Clinical laboratory values

LAMBDA

Clinical laboratory values will be compared to their reference ranges. Values outside the normal ranges will be highlighted. The Investigator has to comment, whether the abnormality is clinically relevant.

Other safety parameters

All results of vital sign measurements will be presented in individual listings. Where appropriate, results and possible changes in parameters will be evaluated descriptively or by descriptive statistics (mean, SD, median, range). Descriptive statistics (N, n, mean, SD, median, minimum and maximum) will be presented for absolute and change from baseline values of vital signs parameters at each timepoint.

Demographic data will be shown in tables as mean values, SD and ranges (min, max).

Clinical laboratory data will be shown in tables as mean values, SD and ranges (min, max) as applicable.

Physical examination, 12 lead ECG, Chest X-Ray performance and concomitant medication will be presented in data listings.

Protocol deviations

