14.1 Demographic Data

14.1.1 Demographic data and baseline characteristics (Randomized set)

Lambda Therapeutic Research Ltd.

Confidential

Project No. 0110-23

Table No. 14.1.1

Demographic data and baseline characteristics (Randomized set)

	Statistics	TRTR (N=xx)	RTRT (N=xx)	Total (N=xx)	p-value
Age (years)	n	XX	XX	XX	X.XXXX
	Mean (SD)	xx.x (xx.xx)	xx.x (xx.xx)	xx.x (xx.xx)	
	Median	XX.X	XX.X	XX.X	
	Min, Max	XX.X, XX.X	XX.X, XX.X	XX.X, XX.X	
Gender					-
Male	n (%)	xx (xx.x)	xx (xx.x)	xx (xx.x)	
Female	n (%)	xx (xx.x)	xx (xx.x)	xx (xx.x)	
Race					
Asian	n (%)	xx (xx.x)	xx (xx.x)	xx (xx.x)	-
American Indian or Alaska Native	n (%)	xx (xx.x)	xx (xx.x)	xx (xx.x)	
Other	n (%)	xx (xx.x)	xx (xx.x)	xx (xx.x)	
Ethnicity					
Not Hispanic or Latino	n (%)	xx (xx.x)	xx (xx.x)	xx (xx.x)	_
Hispanic or Latino	n (%)	xx (xx.x)	xx (xx.x)	xx (xx.x)	
Not Reported	n (%)	xx (xx.x)	xx (xx.x)	xx (xx.x)	
Unknown	n (%)	xx (xx.x)	xx (xx.x)	xx (xx.x)	
Height (cm)	n	xx	xx	XX	x.xxxx
	Mean (SD)	xx.x (xx.xx)	xx.x (xx.xx)	xx.x (xx.xx)	
	Median	XX.X	XX.X	XX.X	
	Min, Max	xx.x, xx.x	XX.X, XX.X	xx.x, xx.x	

Project No. 0110-23 Version 00

Lambda Therapeutic Research Ltd.

Confidential

Project No. 0110-23

Table No. 14.1.1

Demographic data and baseline characteristics (Randomized set)

	Statistics	TRTR (N=xx)	RTRT (N=xx)	Total (N=xx)	p-value
Weight (kg)	n	XX	XX	XX	x.xxxx
	Mean (SD)	xx.x (xx.xx)	xx.x (xx.xx)	xx.x (xx.xx)	
	Median	XX.X	XX.X	XX.X	
	Min, Max	xx.x, xx.x	xx.x, xx.x	xx.x, xx.x	
BMI (kg/m²)	n	xx	xx	xx	x.xxx
	Mean (SD)	xx.x (xx.xx)	xx.x (xx.xx)	xx.x (xx.xx)	
	Median	XX.X	XX.X	XX.X	
	Min, Max	XX.X, XX.X	xx.x, xx.x	XX.X, XX.X	

N = Number of subjects in safety set, n = Number of subjects in respective categories Note: Percentages are calculated based on the total number of subjects in each category. Treatment specification -> T = Test Product and R = Reference Product. p-value is calculated using an independent t-test. Reference Listings: 16.2.1.3, 16.2.4.1, 16.2.9.3

Output Generated on: DDMMMYYYY hh:mm

<Note: Repeat the same table as 14.1.2 for Safety set and 14.1.3 for PK set >

Project No. 0110-23 Version 00

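### SAP shell 14.3.6 prints unadjusted t-test p-values for vital signs that both documents' text treats as descriptive; about 3 of 60 post-dose results would fall below 0.05 by chance

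*SAP*

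**What the plan says.** **Protocol.** Vital signs, absolute and as change from baseline, are a secondary safety endpoint (section 3, Table 4). The safety estimand's summary measure for them is a list of descriptive statistics: counts, mean, SD, median and range. Section 9.4.4 repeats this, saying that descriptive statistics "will be presented for absolute and change from baseline values of vital signs parameters at each timepoint", and leaves the fuller description of the safety analyses to the SAP.

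**SAP text.** Section 7.2 says that safety results, with vital signs named among them, "will be listed and evaluated descriptively". It gives the same descriptive list for vital signs. The only p-values it announces (chi-square or Fisher's exact) are for adverse-event data. Demographics are to be shown as mean, SD and range. Section 8 lists one change from the protocol, the ANOVA model.

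**SAP shells.** Shell 14.3.6 has columns for TRTR, RTRT, total and p-value. The p-value is filled at screening and at each visit and time point shown, with the footnote "P-value is calculated using an independent t-test". A programmer's note extends the layout: "This table will continue for vital parameters like Systolic Blood Pressure (mmHg), Diastolic Blood Pressure (mmHg), Oral Body Temperature (°F), etc". The companion shells for change from baseline (14.3.7) and quantitative laboratory values (14.3.8) have no p-value column. Shell 14.1.1, repeated as 14.1.2 and 14.1.3, prints p-values for age, height, weight and BMI under the footnote "p-value is calculated using an independent t-test".

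**The concern.** Outputs are programmed from the shells, so tests that the text does not plan would still reach the study report. Three things are unsatisfactory.

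- A named secondary endpoint that both documents describe without testing acquires a large set of tests. They have no stated level, no adjustment and no label saying how to read them.
- The tests do not address the safety objective, which is Test versus Reference. They compare sequences one time point at a time and make no use of the within-participant comparison that the crossover provides. The screening and Period I pre-dose rows precede any dosing and can say nothing about either product.
- With this many tests, some small p-values are expected when the products do not differ, and a reader of the safety section has no guidance on discounting them.

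**Working it through.** The documents give no error rate for this table, so there is no planned figure to reproduce.

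**Inputs**

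- Parameters read after dosing: systolic pressure, diastolic pressure and pulse, i.e. 3 (Protocol 8.3.2). Temperature and respiratory rate are taken only at screening, check-in and check-out (Protocol 8.3.1) and are not counted.
- Times: pre-dose "and at 2, 4, 6, 12 and 24 hours post-dose in each period", i.e. 5 post-dose readings.
- Periods: "this study will employ 2 sequences in a 4-period cross-over design", i.e. 4.
- Group size: 70 participants (Protocol 9.6) with equal allocation (6.3), i.e. 35 per sequence.
- Level: 5% two-sided, **assumed**. SAP 6.3.2.2 states 5% for the pharmacokinetic ANOVA only.

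**Number of tests and expected chance results**

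- Post-dose tests: 3 × 5 × 4 = 60. Expected below 0.05 with no product difference: 60 × 0.05 = 3.0.
- With the pre-dose rows: 3 × 6 × 4 = 72. Expected: 72 × 0.05 = 3.6.

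An expected count is a sum of individual probabilities, so correlation between readings does not change it.

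**Chance of at least one below 0.05 among the 60**

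If the tests were independent: 1 − 0.95^60 = 0.954. Repeated readings on one participant are positively correlated, which lowers this figure, so it is an upper bound.

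The documents give no correlations, so a range was simulated: 35 versus 35, multivariate normal, no product difference, pooled t-test, 3,000 trials per setting. The between-participant share is the correlation between readings of one parameter in different periods. Each range covers systolic–diastolic correlations from 0 to 0.8 and pulse–pressure correlations from 0 to 0.3.

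| Between-participant share | Within-period correlation | P(at least one p<0.05) |
|---|---|---|
| 0.3 | 0.5 | 83–87% |
| 0.5 | 0.5 | 74–81% |
| 0.6 | 0.7 | 65–71% |
| 0.7 | 0.8 | 53–61% |
| 0.8 | 0.8 | 50–52% |
| 0.8 | 0.9 | 43–50% |
| 0.9 | 0.9 | 33–38% |

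Across all settings run, the mean number of results below 0.05 was 2.8 to 3.3, in line with 3.0. Simulation error near 50% is √(0.25/3000), about 0.9 percentage points, so the 0.8/0.8 row cannot be told apart from one half.

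**Direction of the contrast**

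Let d be a chance difference, TRTR minus RTRT, that persists through the study. The shell shows +d in every period. TRTR takes T in periods I and III and R in II and IV, so read as Test minus Reference this is +d, −d, +d, −d.

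**The case against.** **The protocol delegates safety detail to the SAP.** Protocol 9.4.4 does so, and SAP 7.2 describes its summary statistics in open-ended terms. This stands in part: the defect is better described as a shell that disagrees with the SAP's own text than as a breach of the protocol, and silence in SAP section 8 is only supporting evidence. It does not remove the point, because SAP 7.2 is specific about where p-values belong, and vital signs are not included.

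**No claim depends on these p-values.** This stands. No level is stated for the table, and a family-wise error rate matters most when rejection leads to a claim. That limits the consequence.

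**Stronger readings that a reader might infer, and that the documents do not support**

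- *A significant result is more likely than not, whatever the data.* This depends on a within-participant correlation that neither document gives. It held in every setting tried with a share up to 0.7 and fails at about 0.8 and above. For the same reason no fixed multiple of 5% serves as a floor.
- *Chance results would cluster and resemble a consistent product effect.* They can cluster, but a persistent sequence imbalance reverses its Test-versus-Reference direction each period. It would look like a sequence difference.
- *SAP 6.2 wrongly exempts safety tests.* Its sentence, "No multiplicity adjustment is required for this bioequivalence study", follows the bioequivalence hypotheses and sits in the section on pharmacokinetic analysis. It need not be read as covering safety.
- *Every significant baseline p-value is chance by design.* This is true of the randomised set, but not strictly of the PK set in shell 14.1.3, whose membership depends on post-dose data.
- *Adding check-in and check-out rows gives a much larger count.* The documents do not say whether check-out vital signs are separate from the 24-hour reading, so the count here stays with the scheduled post-dose readings.

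**Conclusion.** The point holds as an inconsistency between a table shell and the text of both documents, in a named secondary endpoint. The firm part is textual: the analysis is described as descriptive, p-values are announced for adverse events only, and shell 14.3.6 prints them for vital signs.

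At an assumed 5% level, 60 post-dose tests give about 3 chance results below 0.05 when the products do not differ, at any correlation. The chance of at least one is about 75–80% at a between-participant share of 0.5, about 55–60% at 0.7, and about half or less at 0.8 and above. The independence figure of 95% is an upper bound, not the likely rate. These probabilities rest on assumed shares and on normally distributed readings with no carryover.

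The consequence is confined to safety reporting. The bioequivalence decision uses none of these p-values. The change should be made before programming because it restores the stated analysis at almost no cost.

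**What to change.** - Delete the p-value column and the t-test footnote from SAP shell 14.3.6, so that it matches shell 14.3.7 and SAP 7.2.
- Delete the p-value column and t-test footnote from shells 14.1.1, 14.1.2 and 14.1.3, because SAP 7.2 gives demographics as mean, SD and range only.

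SAP 6.2 needs no change for this point. The cost is an edit to the shells before programming, with no effect on participants, data collection or power. What is lost is a set of p-values that neither document's text asks for.
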